#### D. RISKS AND BENEFITS:

The risks of anthropometric measurements are discomfort and emotional upset. For accelerometry in particular there may be a perceived risk of external monitoring or "tracking". Accelerometer data is not generated through real-time tracking and the location of participants is not recorded by the device. Data collected by the accelerometer can only be accessed when the device is returned and accessed via specialized proprietary software. If the device is lost or stolen, it is extremely unlikely that data could be accessed. If accessed, participant information other than activity data would *not* be available. The only risk of the surveys and of EHR data extraction is breach of confidentiality. The risk of the home visit for data collection is breach of confidentiality and discomfort with having study staff enter the home. Breach of confidentiality will be strictly guarded against, and any unintentional breach of confidentiality would not be anticipated to affect the employability, reputation, or financial status of a participant.

The primary risk of follow-up interviews is breach of confidentiality and will be strictly guarded against, and any unintentional breach of confidentiality would not be anticipated to affect the employability, reputation, or financial status of a participant. Additionally, participants may also feel uncomfortable providing negative feedback about Community-AHF or its implementation.

**Protection Against Risk** – The primary risk across all aims is breach of confidentiality. We will ensure that personally identifiable information, including lists of potential participants, will be stored in secure environments. Documents, interview transcripts and survey data will be stored in locked file cabinets and data will be stored on secure computers protected by University of Colorado (CU) and Johns Hopkins University security protocols. Both institutions have state-of-the-art information technology to assure high security in data storage and transfer. No identifiable data will be stored on personal computers or devices. The proposal will be reviewed and approved by COMIRB prior to any work being done. We will take the following additional steps to protect privacy and confidentiality:

- Only the study team will have access to identifying information.
- Each study participant will be assigned a unique identification (ID) number at the time of recruitment to de-identify their name from data. The database linking the ID with the participant will only be accessible to select research staff (Multi-PI, site research coordinator, data manager)
- Audio files will be uploaded within 24 hours to a secure network drive that is password protected and backed up regularly.
- After uploading the audio file, it will be deleted from the recorder.
- Once transcribed by professional transcription services that meet HIPAA privacy and confidentiality standards, textual
  data will be uploaded to this same server and only analyzed from password-protected devices that can access this
  server.
- For the surveys, individual subjects' survey responses will be confidential through the use of REDCap.

**Benefits** – There are many potential health benefits to participants in endeavoring to reduce child BMI, including lower adult cardiovascular disease risk. Although past research has demonstrated benefit from receiving the type of intervention that we will deliver in this trial, confirmed benefit from participating in this research cannot be claimed, as we are testing an adaption of an evidence-based intervention in new communities. Regardless of intervention effectiveness, the potential benefits for the study participant include receiving information regarding healthy behaviors and positive parenting skills. Given that the risks are minimal and the potential for positive health benefits, we believe that the benefits of the proposed project far outweigh any risks.

### **E. POTENTIAL SCIENTIFIC PROBLEMS:**

Likewise, some dyads will not wish to complete all aspects of the pilot study. We will work with families to complete measures that they feel comfortable with. Acceptance or denial of study procedures will provide important information for a future larger scale trial.

### F. DATA ANALYSIS PLAN:

### Indicators of Effectiveness

As this is a pilot study, we will not be powered to detect statistically significant differences pre- and post- intervention. We will measure the average change in %BMIp95 between baseline and completion of the Community-AHF active phase. Without a counterfactual (control group) we will not be able assign responsibility to Community-AHF for any observed

improvements. Change in %BMIp95 across the study period will provide data to test our hypotheses and will inform statistical power analyses for a subsequent trial. This pre- and post-intervention data is ideal for generating sample size estimates for a larger randomized control trial in the same population.

We will conduct within-individual analyses for each outcome of interest. We will only analyze participants who contribute pre and post measures in order to avoid biases that can occur when analyses are conducted with all available data. For each outcome for which a participant contributes pre and post measurements, we will calculate pre and post means, standard deviations, differences in means and the p-value of the difference. We will conduct preliminary analyses of outcomes according to subgroups defined by rate of attendance at intervention sessions. If adequate data are available, we will explore the possibility of a nonresponse analysis.

All statistical analyses will be conducted using Mplus, or the latest version of R (specifically the nlme package).

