#### I. HYPOTHESES AND SPECIFIC AIMS:

This Human Subjects Research involves a pilot trial using a pre/post design to simultaneously to evaluate the feasibility, acceptability, and preliminary effectiveness of a weight management intervention, Community Active and Healthy Families (Community-AHF), at reducing child body mass index (BMI).

Study Aim: To pilot Community-AHF among 5–12-year-old overweight and obese Latino children in immigrant families (n=40 parent/child dyads) using a pre/post design

- We will examine changes in child BMI (primary outcome) and in diet, physical activity, and parenting skills/stress (secondary outcomes) pre- and post-intervention to assess for indicators of intervention effectiveness and to gather the information needed to refine measures, and measurement procedures in preparation for a pragmatic randomized controlled trial.
- We will evaluate pilot implementation via assessing program acceptability and feasibility. We hypothesize that families
  will report high levels of program acceptability and that implementing community organizations/clinics will report high
  levels of program feasibility and an intention to maintain participation in a future trial. We will also conduct qualitative
  interviews to explore implementation successes and challenges to guide refinement of implementation protocols for a
  future trial.

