# C. STUDY DESIGN AND RESEARCH METHODS:

# Study Design:

We will recruit child-parent dyads from one primary care pediatric practice in both CO and MD or via outreach by our community partner in CO. We will recruit 20 child-parent dyads at each site. We will enroll 40 overweight (BMI≥85th%ile for age and sex) or obese (BMI≥95th%ile for age and sex) 5–12-year-old patients and a parent/guardian. We will examine changes in the anticipated trial outcomes. We will assess intervention acceptability and feasibility to parents and examine preliminary effectiveness. The primary effectiveness outcome will be a change in BMI from baseline to follow up. Secondary outcomes reflect key features of the intervention curriculum that promote child and family behavior change including child diet and PA, home food environment, parent PA promotion and parenting self-efficacy. We will also conduct a preliminary implementation evaluation. If two (2) children in the same household are eligible, one will be randomly selected to be in the index child participant.

Community AHF is a 10-month intervention with 20 contact hours (16 in person during the active phase and 4 virtual during the maintenance phase). Each index child participant must be accompanied by a parent; additional parents/caregivers and siblings of the index child may attend. This pilot will evaluate the active phase of the intervention *only* given the time constraints of this funding mechanism. Effectiveness data for the evidence-based intervention from which Community-AHF was adapted is based on the 4-month active phase.  During the 4-month active phase participants attend eight 2-hour semimonthly group education sessions. Sessions follow a curriculum and provide: 1) Practical information to increase knowledge and perceived importance of healthy diet and PA practices; 2) Skill building in problem-solving and positive parenting to overcome barriers to behavior change at the child and family-level; 3) PA; and 4) Facilitated supportive discussion to assist parents in managing stressors and SDOH barriers to healthy weight.

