Each session covers specific objectives and includes complementary hands-on activities and breakout groups for children (children's breakouts are often conducted in English). At the conclusion of each session participants receive take-home materials to facilitate behavior change. Sessions are co-facilitated by a registered nurse and CHW. Additionally, participants complete 7 CHW coaching calls (15-20 minutes) during weeks without a group session to reinforce change goals and discuss successes and challenges meeting these goals. During the 6-month maintenance phase which will be employed in a future trial, participants will complete monthly, 20-minute coaching calls, attend a primary care obesity follow-up visit, and attend a concluding celebration. Community-AHF will be delivered by trusted community organizations well-known to the local Latino community and experienced in providing community programming.

We will also complete a qualitative evaluation of the Community-AHF pilot and its implementation. We will interview a subset of parents and youth who participate in the intervention for this portion. These interviews will take place after the completion of the pilot.

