### Research Methods:

Pilot dyads will complete the active phase of the Community-AHF intervention that includes eight (8), semimonthly 2-hour group education sessions for 16 weeks, and 8 biweekly coaching calls. Sessions follow a curriculum and provide: 1) Practical information to increase knowledge and perceived importance of healthy diet and physical activity practices; 2) Skill building in problem-solving and positive parenting to overcome barriers to behavior change at the child and family-level; 3) Physical activity; and 4) Facilitated supportive discussion to assist parents in managing stressors and social determinants of health barriers to healthy weight. Each session covers specific objectives, includes a number of complementary, handson activities, and provides participants with take-home materials to facilitate behavior change. Community-AHF will be delivered by a nurse and a Community Health Worker (CHW) trained by a consultant nutritionist and study investigators.

If the child has been referred by their pediatrician referring providers will also receive a communication regarding the family's participation. Once the child starts a cohort there will be an additional communication to the referring provider when the child completes the 4-month active phase. This communication will include a summary of family goals for healthy child weight, the current BMI, and a reminder that the child should have a follow up visit with the referring provider. The consent process will include specific permission for this release of information to the referring provider and/or signing of a separate release of information of form based on IRB determination.

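### The pre/post p-values make no allowance for delivery in group cohorts at two sites, and the plan to size the next trial from these data does not mention clustering

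*Combined protocol and SAP*

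**What the plan says.** The design has three features that group the children. Section C (Study Design) sets two sites: "We will recruit 20 child-parent dyads at each site", which gives the total in section I, "in immigrant families (n=40 parent/child dyads) using a pre/post design". Delivery is in groups: "During the 4-month active phase participants attend eight 2-hour semimonthly group education sessions", and "Sessions are co-facilitated by a registered nurse and CHW". The sessions include facilitated discussion among parents. The Research Methods text shows that families enter in cohorts: "Once the child starts a cohort there will be an additional communication". Neither the number of cohorts nor their size is given.

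The quantitative plan is in section F, Indicators of Effectiveness: "We will conduct within-individual analyses for each outcome of interest". For each outcome it lists pre and post means, SDs, the mean difference and a p-value. No site term, cohort term, random effect, ICC or cluster-robust error is written. Mplus and the R package nlme are named as software, but no model is specified. Site is used only to organise the qualitative summaries.

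Section F says that the pilot is not powered for significance and that, without controls, change cannot be credited to the programme. It also says that the change data will be used to test hypotheses, and adds: "This pre- and post-intervention data is ideal for generating sample size estimates for a larger randomized control trial in the same population". Clustering is not mentioned there.

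**The concern.** Children in one cohort share sessions, peers, a calendar period and facilitators. Their changes in BMI, diet or activity may therefore resemble each other more than those of children in different cohorts. Households are not a source of this, because one index child is taken per household; cohorts remain one.

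A paired test on 40 changes treats them as 40 independent observations. If the cohort ICC is positive, the standard error for inference beyond these particular groups is too small and the p-value is too small with it. The plan produces such a p-value for every outcome. Section G looks beyond these groups, since it expects the study to settle whether community-based weight management can work in Latino children.

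The second stake is the next trial. If it delivers the programme in groups and is sized from the pilot SD alone, it would fall short of its intended power.

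**Working it through.** **Inputs from the documents.** 2 sites × 20 dyads = 40, which agrees with the stated total. There is one index child per household and one paired change per child per outcome. The plan gives no power, effect size, SD or ICC, so there is no power figure to reproduce.

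**Assumptions.** ICC of change 0.01, 0.05 and 0.10; cohort size m of 5, 10 or 20 (8, 4 or 2 cohorts).

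**Formulas.** Design effect DE = 1 + (m − 1) × ICC. Effective n = 40 / DE. Type I error of a nominal two-sided 5% test ≈ 2 × [1 − Φ(1.96 / √DE)].

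Worked example, m = 10 and ICC = 0.05: DE = 1 + 9 × 0.05 = 1.45; √1.45 = 1.204; effective n = 40 / 1.45 = 27.6; 1.96 / 1.204 = 1.628; type I error ≈ 10%.

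| Cohorts | ICC | DE | √DE | Effective n | Type I error |
|---|---|---|---|---|---|
| 8 of 5 | 0.01 | 1.04 | 1.02 | 38.5 | 5.5% |
| 8 of 5 | 0.05 | 1.20 | 1.10 | 33.3 | 7.4% |
| 8 of 5 | 0.10 | 1.40 | 1.18 | 28.6 | 9.8% |
| 4 of 10 | 0.01 | 1.09 | 1.04 | 36.7 | 6% |
| 4 of 10 | 0.05 | 1.45 | 1.20 | 27.6 | 10% |
| 4 of 10 | 0.10 | 1.90 | 1.38 | 21.1 | 16% |
| 2 of 20 | 0.01 | 1.19 | 1.09 | 33.6 | 7% |
| 2 of 20 | 0.05 | 1.95 | 1.40 | 20.5 | 16% |
| 2 of 20 | 0.10 | 2.90 | 1.70 | 13.8 | 25% |

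Simulating the one-sample t-test on 40 changes with random cohort effects gives the same figures to within about half a percentage point. At ICC = 0 the test holds its 5%. If 32 children complete (an assumed 20% loss) in 2 or 4 cohorts, the simulated range is about 6% to 22%.

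**Pilot SD of change.** Its expected square is the true variance times 1 − ICC × (m − 1)/(N − 1). At the worst case shown, m = 20 and ICC = 0.10, this is 1 − 0.10 × 19/39 = 0.951, so the SD is about 0.975 of its true value. At m = 10 and ICC = 0.01 the ratio is 0.999. The SD is a sound input to a later calculation.

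**What omitting a design effect would cost the next trial (illustration).** For a trial planned at 80% power, actual power ≈ Φ(2.80 / √DE − 1.96). Take m = 10 and ICC = 0.05.
- Both arms in groups: DE = 1.45, so Φ(2.325 − 1.96) = about 64%.
- Only the intervention arm in groups: average DE = (1 + 1.45)/2 = 1.225, so Φ(2.530 − 1.96) = about 72%.

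At an assumed standardised effect of 0.3, an unadjusted 175 per arm would have to become 175 × 1.45 ≈ 254 or 175 × 1.225 ≈ 215.

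**The case against.** The strongest reply is that this is a pilot that claims neither power nor attribution, and that no progression rule depends on a p-value. The explicit hypotheses in section I concern acceptability, feasibility and willingness to continue, and the survey measures are to be summarised descriptively. This limits the consequence. It does not answer the point, because low power and an anti-conservative p-value are separate problems and the plan still commits to a p-value for every outcome.

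Naming nlme leaves room for a random effect. A reader might infer from the silence that the plan has decided to assume independence. It has not: no model is written either way. But the plan followed as written contains no adjustment.

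The figures rest on cohort sizes and ICCs that the documents do not give. This stands. The larger error rates belong to the largest cohorts, and with cohorts of 5 the rate stays below 10% throughout. The documents also do not say that one nurse and one community health worker lead every cohort.

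A reader might further infer that the next trial will be undersized. The documents do not support that. They show no sample-size calculation, allocation unit, group size or effect size for it, and a design effect could still be applied. Nor is the SD a culprit, as shown above. The plan promises no confidence intervals, so there are no published intervals to call too narrow.

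**Conclusion.** The point holds in limited form. Group delivery in cohorts at two sites is documented, and the analysis plan makes no allowance for it. If the cohort ICC is positive, the p-values are too small. Under assumed ICCs of 0.01 to 0.10, type I error is about 6% to 16% with 4 cohorts of 10, about 7% to 25% with 2 cohorts of 20, and nearer 5% with smaller cohorts. These are conditional figures, not a demonstrated error rate.

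For the next trial the finding is a risk: the plan recommends these data for sample-size work and says nothing of clustering. The power losses shown arise only if the design effect is left out. Since the pilot makes no confirmatory claim, this is a cheap improvement and not a threat to the study.

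**What to change.** Amend section F, Indicators of Effectiveness, as follows.

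1. Report the mean change by site and by cohort, with the number of cohorts and their sizes.
2. Report each mean change with a 95% confidence interval in two forms: unadjusted, and widened by √(1 + (m − 1) × ICC) for ICC 0.01, 0.05 and 0.10, where m is the actual cohort size. Present the p-values as unadjusted for clustering.
3. State that the sample size of the next trial will apply a design effect over the same ICC range to each arm delivered in groups.

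A model with site fixed and cohort random should not be the main remedy. With one cohort per site, the two factors coincide and the cohort variance cannot be estimated. With two per site, only 4 − 2 = 2 degrees of freedom remain for it. The assumed ICC range works in either case.

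The cost is a few sentences and a few extra lines of output, with no new data and no burden on families. The downside is wider intervals and a larger planned sample size.

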# Preliminary Implementation Evaluation

Survey measure results will be summarized using descriptive statistics. Qualitative data from follow-up interviews will be analyzed using rapid qualitative methods as we anticipate a short time frame between obtaining these data and refinement of the implementation protocol in preparation for a future trial if funded. Interview transcripts will be summarized in a template based on the guiding questions to capture key points. Summarizing will be completed by the research team who will resolve differences through consensus. Using matrix analysis techniques, summaries will be categorized by site and participant type (parent, child or community organization staff member). Two research team members will independently identify and group key themes from summaries, and then compare themes. Finally, a saturation grid, which visually aligns support for themes, will be developed to cross-check and confirm evidence of themes against the dataset.

**Data Management** – Audio recordings will be stored in a UC-Anschutz secure encrypted database. REDCap will serve as the storage system for surveys. Only the PI, data analysts, and research staff will have access to the data. All identifiable information will be restricted for contact information only and will be separated from other study data. All identifiable information will be removed from audio recordings and survey data. Consent forms will be stored in a locked cabinet at the sites ACCORDs for Aurora Community Connection and Johns Hopkins Bayview [name]. Due to the nature of the pilot, consent forms will be transferred from the home of the participant to the site. In these cases, the consent forms will not be left unsupervised during transport and will be placed in a locked cabinet immediately upon reaching the site destination. Research staff will minimize additional trips to obtain consent from participants in order to safeguard confidentiality.

**Date Destruction** – Paper consent forms and data stored on servers will be destroyed per HIPAA regulations (7 years after IRB of record acknowledges study closure).

### G. SUMMARIZE KNOWLEDGE TO BE GAINED:

The findings from the proposed research will directly impact pediatric primary care practice and treatment of child obesity. This proposed study will answer a pivotal question about whether community-based weight management can successfully reduce overweight and obesity among Latino children. Overall, the knowledge to be gained by this study is valuable enough that the minimal risks of the study are reasonable in relation.

